1.0 Background

Overview of the Problem: PTSD affects 7-12% of the general population¹⁵ or approximately 21 million Americans¹⁶ who will use health care services frequently for many years. The annual cost of anxiety disorders such as PTSD is substantial, estimated at about \$42.3 billion in the United States.¹⁴ Furthermore, individuals with PTSD are among the most frequent users of healthcare services, with nonpsychiatric direct medical costs (e.g., doctor and hospital visits) estimated at approximately \$23 billion a year.¹⁴ Societal costs include both psychiatric and nonpsychiatric medical treatment, indirect workplace costs, and mortality costs. More than half of these costs are attributed to repeat use of healthcare services to relieve anxiety-related symptoms that mimic those of other physical conditions. Therefore, PTSD is a source of chronic disability for veterans and civilians and costly for the US government in terms of treatment as well as disability payments. Despite some success with currently used medications, many PTSD patients report little meaningful improvement in their symptoms. Furthermore, veterans whose PTSD symptoms have been present for many years pose the particularly complex challenge of being more resistant to the beneficial effects of medications for PTSD symptoms.²⁸ Medications currently used to treat PTSD are of limited effectiveness as they were not designed to target the unique pathophysiology of PTSD, and remain one of many challenges in PTSD treatment.³³ Although there are effective, available PTSD-specific treatments such as Cognitive Processing Therapy and Prolonged Exposure, many PTSD sufferers delay seeking professional help for years to decades.⁴ Such factors as avoidance (one of the three PTSD symptom clusters), fears that directly addressing the trauma will only make matters worse, and the stigma related to PTSD and mental health treatment, are thought to contribute to this reluctance to engage in treatment.⁵ In addition, dropout rates are high for current PTSD treatments and they may not be effective for all evidenced by the significant number who remain symptomatic despite pharmacotherapy and psychotherapy.⁶ Although there are now psychological treatments that can effectively treat individuals with PTSD, the majority of individuals with PTSD, including active duty military personnel, veterans, and civilians, receive treatments of unknown efficacy.³⁴ Unresolved or untreated trauma has been associated with the development of multiple, severe, and persistent physical and mental health problems, substance abuse, future criminal behavior, and social problems.³⁵ Thus there is a need for more effective PTSD treatments options, particularly which do not require direct verbal processing of the trauma but can calm the hyperactive threat system typical of PTSD.

Other treatments are needed when PTSD symptoms are not relieved: The lack of relief from existing treatments can be extremely frustrating to patients who may feel that they have exhausted all options for PTSD treatment. This is also frustrating for VA and other mental health providers concerned about the limited efficacy of medications and lack of additional treatment options. Therefore, novel treatment approaches are needed that have potential for application across multiple VA clinical settings and in the community, to supplement existing services for PTSD care. Increasingly, patients are interested in complementary and alternative medicine (CAM) treatment options.³⁶ This growing interest in CAM is likely multifactorial, involving concerns about limited efficacy of conventional medicine, adverse effects of medications, and avoidance-beliefs related to medications or mental health treatments. CAM treatment options typically have minimal physical and emotional risks, and may allow patients to take a more active role in managing their illness.

Yoga holds promise for PTSD as it combines physical and mental techniques: Yoga therapy is defined by the International Association of Yoga Therapists as “the process of empowering individuals to progress toward improved health and well-being through the application of the philosophy and practice of yoga”.³⁸ Although there are many types of yoga, all involve a combination of stretching exercises and postures with breathing and meditative practices aimed at: (1) lengthening and toning muscles; (2) maintaining flexibility in the joints and spine; (3) increasing oxygenation of the brain; and, (4) training attention and concentration.³⁹ Accumulating research evidence supports yoga as an acceptable and efficacious intervention for those who have experienced trauma, reducing clinician rated⁹ and self-reported PTSD symptoms, symptoms,¹⁰⁻¹² depression¹², anxiety.¹² Research evidence also supports the benefits of yoga in those with other physical and mental health conditions for challenges typical of those with PTSD including increased resiliency to chronic and acute stress^{43,44}, anger-hostility,^{13,45} disturbed sleep.^{46,47} Studies of Mindfulness-Based Stress Reduction (MBSR), an intervention that combines mindfulness meditation with gentle hatha yoga, also provide evidence to support the use of yoga for treatment of trauma.

A trial evaluating holistic yoga for PTSD is timely and needed: Although there has been increased military and VA interest in CAM approaches, such as yoga and meditation, which do not require trauma

processing, research has been limited although promising in terms of acceptability and efficacy.⁷ Our recent search of the ClinicalTrials.com website revealed a total of 10 studies of yoga as an intervention for PTSD (5 completed and 5 current), with such limitations as small samples, uncontrolled or waitlist/usual care controls, and much variation in the style of yoga and components of yoga studied. Thus, randomized controlled trials with large samples to evaluate a standardized traditional holistic yoga intervention are urgently needed to inform VA policy makers and clinicians of what outcomes to expect from a yoga intervention for PTSD. We believe that the proposed trial, “Outcomes of a Holistic Yoga Program Designed to Relieve PTSD” (RELIEVE trial), designed as a large randomized controlled efficacy study of a standardized, traditional holistic yoga intervention (postures, breathing practices, deep muscle contraction practices, relaxation practices), is a significant step beyond previous studies that have evaluated a variety of yoga approaches and/or one yoga component such as relaxation, or yoga as only a part of a mind-body intervention such as Mindfulness-Based Stress Reduction. The Holistic Yoga Program will be documented in a treatment manual and will be taught by teachers registered at least at the 200 hour level with the Yoga Alliance. Additional standardized training and supervision will be provided by an experienced yoga therapist. Thus, if found to be effective, the Holistic Yoga Program and teacher training will have been documented and tested, allowing for swift dissemination and implementation within the VA system.

Significance: PTSD poses enormous public health challenges due to its effects on mental and physical health, and functioning, including interpersonal, social and occupational.³⁴ PTSD is also a critical mental health problem among veterans and constitutes a substantial proportion of the burden of illness among veterans affecting as many as 14 to 16%.¹⁷ Apart from the significant psychological cost to individuals with PTSD and their families, there is a steep financial cost to society, in terms of entitlements and lost productivity. PTSD is the most common psychiatric disorder for which veterans seek and receive compensation and most common cause of disability within the VA system and the U.S.² Although individuals suffering from PTSD desire relief, it is difficult for them to present for treatment due to the avoidance, a hallmark symptom of the disorder. Additional research is desperately needed to find more effective approaches to assisting individuals with PTSD to engage in treatment earlier by providing treatment options that relieve symptoms yet do not require the feared trauma processing. Armed with new skills and some symptom relief from less intense treatment options, those with PTSD may feel more confident to pursue the more intense evidence-based treatments such as Cognitive Processing Therapy, Prolonged Exposure and Cognitive-Behavioral Conjoint Therapy for PTSD.

Yoga, in its traditional, holistic form, is aimed at improving physical, mental and spiritual well-being and involves teaching individuals skills they can practice at home. Yoga has been found to reduce trauma-related symptoms, and thereby may improve the ability of individuals with PTSD to attend to and become aware of their cognitive, emotional and physical states, including dysfunctional thinking and behavioral patterns that contribute to emotional suffering and interfere with effective functioning. Until recently, those who have PTSD have been largely ignored in yoga research. Our proposal is significant as it will be the first large, rigorously designed, randomized, controlled trial comparing a holistic yoga intervention tailored for individuals with PTSD to an attention control. Results of the proposed study may scientifically validate the therapeutic value of yoga as an intervention for veterans with PTSD, in particular, revealing what kinds of clinical and rehabilitation benefits can be expected from augmenting current VA PTSD treatment with a yoga intervention, e.g. reduced PTSD and PTSD-related symptoms, improved well-being, and enhanced quality of life. Results will yield scientifically sound information for policy makers and clinicians in the VA system and those outside the VA system, e.g. health insurers, healthcare delivery systems, clinical researchers, and public education systems (media). Results may provide support for investigating these procedures in other treatment settings, allowing for replication and further refinement. Enhancing current VA trauma services with a yoga intervention holds promise that many veterans may achieve gains who might otherwise fail to benefit from treatment.

2.0 Rationale and Specific Aims

Post Traumatic Stress Disorder (PTSD) has been recently conceptualized as a disorder of impeded recovery that is defined by the primary symptoms of re-experiencing, negative alterations in cognitions and mood, avoidance/numbing, and hyperarousal (DSM-5). While these symptoms are natural reactions to trauma, avoidance of feelings and reminders that continue to signal danger interferes with making sense of the

traumatic event and symptom remission.¹ PTSD constitutes a substantial proportion of the burden of illness among veterans.² The course of PTSD varies in duration of symptoms and level of disability, and many experience disabling symptoms for years.³ Although effective PTSD-specific treatments are available (e.g. Cognitive Processing Therapy, Prolonged Exposure), many of those who have PTSD wait years to decades before seeking professional help, if they seek help at all.⁴ PTSD symptoms such as avoidance, fueled by fears that directly addressing the trauma will worsen symptoms, and the stigma of PTSD and mental health treatment, contribute to delayed engagement in treatment.⁵ In addition, dropout rates are high for current PTSD treatments and they may not be effective for all who suffer from PTSD, as evidenced by the significant number who remain symptomatic despite pharmacotherapy and psychotherapy.⁶ As a result, there has been increased interest within the military and VA leadership, as well as active duty military and veterans, in Complementary and Alternative Medicine (CAM).⁷ CAM approaches, such as yoga and meditation, do not require trauma processing, yet appear to relieve symptoms. Yoga is a holistic system of mind-body practices historically developed as a spiritual discipline that supports a mentally and physically healthy lifestyle and incorporates such elements as physical postures, breathing practices, and meditation.⁸ Accumulating research evidence indicates that yoga practices are acceptable and efficacious for those who have experienced trauma, demonstrating reductions in clinician rated⁹ and self-reported PTSD symptoms,¹⁰⁻¹² as well as depression,¹² and anxiety.¹² However, few studies exist that have evaluated yoga for PTSD and they have involved small sample sizes and are either uncontrolled or waitlist/usual care controlled. In addition, there is much variation among studies in the style and components of yoga interventions, i.e. yoga philosophy, postures (asanas), breathing practices (pranayama), relaxation practices (body scan, Yoga Nidra or yogic sleep), and/or practices that cultivate attention and concentration (meditation).¹³ Thus, a fully powered and rigorous randomized controlled trial (RCT) of a standardized, traditional, holistic yoga intervention is urgently needed to inform VA policy makers and clinicians of the potential benefits of yoga as an adjunct to currently available PTSD treatments.

The Outcomes of a Holistic Yoga Program Designed to Relieve PTSD (RELIEVE trial) is a two-arm parallel group randomized clinical trial. The RELIEVE trial will include 232 individuals with PTSD randomized to one of two groups:

- 1) a 16-week Holistic Yoga Program (HYP) (postures, breathing practices, deep muscle contraction practices, relaxation) or
- 2) a 16-week Wellness Lifestyle Program (WLP) (attention control comprised of low intensity walking with didactics about wellness topics).

The Holistic Yoga Program (HYP) will be taught by experienced yoga teachers registered with the Yoga Alliance (200-hour level), who have received additional military and trauma-related training. Thus, if found to be effective, the yoga intervention and teacher training utilized in this trial will have been documented and tested, allowing for swift dissemination and implementation within the VA system.

Study Aims:

- 1) To compare the interventions' effects (HYP vs. WLP) on overall PTSD symptom severity at 8 weeks (early response), 4 months (immediately post intervention), and 7 months (sustained effects).
- 2) To compare the interventions' effects on specific PTSD symptoms (anger, sleep) and related symptoms and outcomes (well-being/quality of life, depression, anxiety, pain).
- 3) To manualize the Holistic Yoga Program (HYP) and procedure to train experienced yoga teachers to deliver the HYP to individuals with PTSD in order to facilitate future study and dissemination efforts.

Our primary hypothesis is that the Holistic Yoga Program (HYP) will be more effective than the Wellness Lifestyle Program (WLP) in reducing overall PTSD severity measured by the Clinician Administered PTSD Scale (CAPS) and the self-report PTSD Checklist (PCL).

Our secondary hypothesis is that the Holistic Yoga Program (HYP) will be more effective than the Wellness Lifestyle Program (WLP) in improving secondary outcomes including specific PTSD symptoms (anger, sleep), and PTSD-related symptoms and outcomes (well-being/quality of life, depression, anxiety, pain).

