Total Time				55 Min	67 Min	61 Min	117 Min	106 Min

Primary Outcome Measures. The primary outcome measures include the total score from the Clinician Administered PTSD Scale (CAPS)⁶⁵ and the total score from the PTSD Checklist (PCL).⁶⁶ The CAPS is considered the “gold standard” diagnostic tool for PTSD assessment by the National Center for PTSD and has been extensively used and validated in clinical trials.^{68,69} The CAPS is a semi-structured clinician interview that measures PTSD diagnostic status and symptom severity consistent with the Diagnostic and Statistical Manual of Mental Disorders (5th ed.).⁶⁷ The CAPS yields both continuous and dichotomous scores for current PTSD symptoms. PTSD self-reported symptom severity will be assessed with the PTSD Checklist, a 20-item self-report measure of the DSM-5 symptoms of PTSD used as a measure of change in PTSD symptoms as a function of treatment. The PCL has demonstrated sensitivity and specificity >70%.^{66, 69, 70} The DSM-5 versions of these measures are not yet normed but should be available for use in this study.

PTSD-Specific Symptoms: The Medical Outcomes Study 12-item Sleep Scale (MOS) will assess **sleep quality** (sleep disturbance, adequacy of sleep, and sleep quantity) and has demonstrated good psychometric properties.⁷⁴ **Anger** will be assessed by the PROMIS Item Bank v. 1.1 – Emotional Distress - Anger - Short Form 5a. PROMIS stands for the NIH Patient Reported Outcome Measurement Information System which provides questions to produce numeric values which indicate patients' state of wellbeing or suffering as well as their ability or lack of ability to function that have been psychometrically validated..

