8.0 Statistical Considerations

RELIEVE will involve a 2-arm, parallel group, RCT. Since participants cannot be blinded to treatment assignment, observed outcomes (if positive) could be affected by expectation bias. To account for this potential bias, we will assess treatment expectations at baseline and account for them in our analyses. We will

randomize at the patient level rather than the provider level for two reasons (1) randomization at patient level saves sample size; and (2) patients from the same provider in the two arms will be adjusted for “provider effect.” Contamination will also be low because there is relatively minimal involvement required of VA providers in RELIEVE. In addition, randomization will be stratified by veteran and non-veteran status and gender (4 strata) to avoid potential imbalance of these factors between the two arms. [name], PhD (statistician) will create a randomization scheme in REDCap for each of the four strata to randomize patients in blocks of 4 assignments within each of 4 stratum.

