Sample size. Our sample size is calculated based on estimated differences of intervention effects between two arms on the primary outcome: CAPS total score at 4 months, or treatment end. The CAPS total score is a continuous measure (0-136) and reflects a combined score reflecting symptom frequency and symptom severity. A recently published yoga pilot study for patients with PTSD⁹ found a pre-treatment CAPS score of 77.33 (standard deviation = 28.6). Post-treatment scores were reduced by 34% (CAPS = 51.1, SD = 27.6, effect size = 0.9) from the yoga intervention. We powered on a medium effect size of 0.55 which requires a larger sample size than 0.9. We recognize the correlation of outcomes from subjects within the same yoga class may reduce the effective sample size compared to the same sample with independent observations. This possible “clustering effect” has implications for power. Randomization will occur at the individual not cluster or clinic level. Also, we expect that the intra-cluster correlation (ICC) will be near zero because groups will have a mixture of participants from the various recruitment sites: therefore, there is no reason to believe that participants within groups would be more correlated on the outcomes than participants from different groups. We have no preliminary data to estimate the intra-cluster correlation (ICC) for participants within the same group. However, based on similarly designed published studies, we expect the ICC to be relatively small and balanced across the two treatment arms since the cluster sizes will be similar. We will assume an ICC of 0.05 for both groups. We will also assume a 20% difference between treatment groups. The absolute score difference at 4 months is estimated to be approximately 15.4 points (61.6, 80% of 77). Assuming a common standard deviation of 28 and using a two-sample t-test, we will need 60 evaluable subjects in each arm to detect such a difference (Cohen’s $d = 0.55$) with >85% power and 5% Type I error rate. With approximately 8 subjects per treatment group/class session or cluster, the design effect is $1 + (8-1) \times 0.05 = 1.35$. Therefore, we will inflate our sample size by 35% to accommodate the potential clustering effects. We then need 81 evaluable subjects in each arm. With an assumed 30% attrition, we will then need $(81 \times 2) / 0.70 = 232$ subjects (116 in each arm).

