Data analysis: Baseline characteristics of the RELIEVE sample. To evaluate representativeness, we will compare enrollees and those who decline enrollment on baseline characteristics (socio-demographic variables, psychiatric comorbidity, and current and prior PTSD treatments). Any differences will be considered when interpreting results of subsequent analyses. We will also examine differences in baseline characteristics between patients who remain in the study and those who dropout. The linear mixed modeling approach (see next section) will ensure that all available data are used for subjects who have missing data. The models will also incorporate dropout status to adjust for follow-up missing data pattern. All participants will have baseline data. The possible missing data patterns will be (1) missing 4 month, not 7 month, (2) missing 7 month, not 4 month, (3) missing both 4 and 7 months, and (4) complete data.

Main analysis of the primary outcome. Our main analysis will use the ANCOVA (analysis of covariance) approach to linear mixed modeling of repeated measures in which the baseline measure of the relevant outcome scores (i.e., CAPS or PCL) is adjusted as a covariate in the model.⁸⁵ The model for CAPS will be adjusted for baseline CAPS score. The model for PCL, a continuous measure with a possible range of 17-85, will be adjusted for baseline PCL score. The CAPS and PCL are measured at every time point (baseline, 8 weeks, 4 months, 7 months) except the CAPS is not administered at 6 weeks in order to reduce participant burden, since the CAPS and PCL are highly correlated. We plan an intent-to-treat analysis with the primary endpoint at 4 months and evaluation of “early” response at 8 weeks and “sustained” response at 7 months (3 months post-intervention). The models will simultaneously incorporate three post-baseline measures (8 weeks ([PCL only], 4 months, and 7 months) of the relevant response variable. The main predictors will be group (treatment arm), time (categorical with indicator variables to avoid restrictive assumption of linearity over time), and their interaction. A random intercept will be used to adjust for the potential clustering effect for patients in

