a specific yoga group. And a subject-specific random intercept (nested within the group effect) will accommodate the correlation among repeated measurements from the same patient. Aim 1 will involve testing intervention effects by using the appropriate contrast from the model to test the difference in CAPS score and PCL score between the two treatment arms at 8 weeks (early response), 4 months (the primary end point which occurs immediately post intervention), and 7 months (sustained effect of intervention). Descriptive statistics including adjusted means, SD, and effect sizes (differences between two arms on adjusted means divided by pooled SD) will be reported for outcomes at each time point. Variables that are either known, or shown with our data, to be significantly correlated to the outcomes, will be considered as covariates, irrespective of their degree of baseline imbalance between randomized groups (e.g., combat vs. con-combat PTSD, baseline credibility score, and mTBI).

Secondary analysis of primary outcome. For the CAPS and PCL total scores, we will also report a clinically relevant descriptive statistic in which we define the patients with more than 30% reduction from baseline as “responders.” We will then compare the probability of responders between treatment arms using a generalized linear mixed model with a logit link. The responding status of each patient at 8 weeks (for PCL only), 4 months and 7 months will be used as the outcome variables. Main predictors are group (treatment arm), time (8 weeks for PCL only, 4 months and 7 months) and their interaction. A significant coefficient of group indicates a significant odds ratio of being a responder between the two arms.

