Analysis of secondary outcomes. Since RELIEVE is not specifically powered for secondary outcomes, these results should be interpreted cautiously unless they are highly significant ($p < .001$). PTSD-specific symptoms (anger, sleep) and PTSD-related symptoms/outcomes (well-being/QOL, depression, anxiety, pain) will be analyzed using the linear mixed modeling approach described above for the primary outcome. The secondary outcomes will be PTSD-specific symptoms including: anger (STAXI score), sleep (MOS score) and PTSD-related symptoms/outcomes: depression (BDI score), anxiety (STAI score), well-being/QOL (SF-12), and pain (BPI). Since there will be a number of secondary outcomes, we will adjust for multiple-comparisons by using the false discovery rate (FDR)⁸⁶ method to control the overall false positive rate at 0.05. Exploratory analyses of potential mediators/moderators: interoceptive awareness and self-regulation. Moderation effects will be assessed by testing two-way interactions between intervention group membership and demographic and baseline scales including treatment credibility, interoceptive awareness, self-regulation and type of trauma (combat vs non-combat related), mTBI. Mediation effects will be analyzed using the MPLUS structural equation modeling (SEM) software to test the direct, indirect, and total effects of paths in a multilevel SEM model that includes potential mediators measured at various study points (see table of measures) including client satisfaction, interoceptive awareness and self-regulation. Adherence to the interventions and home practice will also be assessed for its dose-response effects on the primary and secondary outcomes.

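### CAPS and PCL are both named primary, the trial is sized on CAPS at 4 months alone, and no rule says how the two 4-month tests decide the primary hypothesis

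*Combined protocol and SAP*

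**What the plan says.** Three parts of the document describe the primary outcome, and they do not agree.

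- **Section 2.0, primary hypothesis.** Yoga is expected to do better than the wellness programme "in reducing overall PTSD severity measured by the Clinician Administered PTSD Scale (CAPS) and the self-report PTSD Checklist (PCL"). This is one hypothesis with two measures.
- **Section 5.0, Primary Outcome Measures.** The plural is used: "The primary outcome measures include the total score from the Clinician Administered PTSD Scale" and, in the same sentence, the PCL total.
- **Section 8.0, Sample size.** The singular is used. The calculation rests "on the primary outcome: CAPS total score at 4 months, or treatment end", and 60 evaluable participants per arm are said to detect the difference "with >85% power and 5% Type I error rate". No effect size, SD or power is given for PCL.

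Section 8.0 then fixes the time point under its main-analysis heading ("We plan an intent-to-treat analysis with the primary endpoint at 4 months") and uses model contrasts "to test the difference in CAPS score and PCL score between the two treatment arms at 8 weeks (early response), 4 months" and 7 months. The responder analysis that follows again treats both totals as the primary outcome.

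The one multiplicity provision is for other endpoints: "Since there will be a number of secondary outcomes, we will adjust for multiple-comparisons by using the false discovery rate" method. PCL is not in the list of secondary outcomes given there.

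**The concern.** Two measures are tested at the primary time point, and nothing says how the two results combine. Three readings are open: CAPS alone decides, either measure is enough, or both are needed. They have different error rates and different power, and the stated 5% and 85% belong only to the first. If CAPS and PCL disagree at 4 months, the rule could be chosen after the results are known.

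Disagreement is plausible because the measures are not equally protected from bias. Sections 4.0 and 5.0 have a blinded research assistant conduct the CAPS interviews, whereas PCL is completed by participants who know their programme. Section 8.0 recognises expectation bias and responds: "To account for this potential bias, we will assess treatment expectations at baseline and account for them in our analyses". That may reduce the bias, but it is not a success rule. A win on PCL alone is the result most exposed to this bias, and the plan does not say what such a win would mean.

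**Working it through.** **Inputs from Section 8.0.** Difference 15.4 points, SD 28, so d = 15.4/28 = 0.55; 5% Type I error; power above 85%; ICC 0.05; 8 per class; 30% attrition.

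**Assumptions.** Testing is taken as two-sided; the plan does not say so, but this reproduces its n. The plan calls CAPS and PCL strongly correlated without giving a figure, so the correlation ρ between the two test statistics is varied from 0.5 to 0.9. PCL's standardised effect is not given; 0.55 is used first and then varied.

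**1. The plan's own figure.**
- n per arm = 2(1.960 + 1.036)²/0.55² = 59.4, rounded up to 60.
- Power at 60 per arm: noncentrality 0.55 × √(60/2) = 3.012, and Φ(3.012 − 1.960) = 85.4% (84.8% with the t distribution).
- Design effect 1 + 7 × 0.05 = 1.35; 60 × 1.35 = 81 per arm; 162/0.70 = 231.4, so 232.

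The arithmetic reproduces, for CAPS alone.

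**2. Either win counts.** Under the null the two statistics (Z₁, Z₂) are bivariate normal with correlation ρ.

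| ρ | False result favouring yoga, P(Z₁ or Z₂ > 1.96) | Either direction, P(\|Z₁\| or \|Z₂\| > 1.96) |
|---|---|---|
| 0.5 | 4.5% | 9.1% |
| 0.7 | 4.2% | 8.3% |
| 0.8 | 3.9% | 7.8% |
| 0.9 | 3.5% | 7.0% |
| One test | 2.5% | 5.0% |

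**3. Both must win.** Type I error is not inflated. Power is P(Z₁ > 1.96 and Z₂ > 1.96) with the noncentralities below.

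*Unadjusted, as in the sample size section.* Noncentrality is 3.012 for both measures, with an effective 81/1.35 = 60 per arm. Power is 76.3%, 78.3%, 79.6% and 81.3% for ρ = 0.5, 0.7, 0.8 and 0.9, against 85.4% for CAPS alone.

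*With the planned baseline adjustment.* Noncentrality becomes 3.012/√(1 − r²), where r is an assumed baseline-to-follow-up correlation, taken as equal for both measures.

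| r | Noncentrality | CAPS alone | Both, ρ = 0.5 to 0.9 |
|---|---|---|---|
| 0.3 | 3.158 | 88.5% | 80.9% to 85.0% |
| 0.4 | 3.287 | 90.8% | 84.4% to 87.8% |
| 0.5 | 3.479 | 93.6% | 88.9% to 91.3% |

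*If PCL's effect differs (unadjusted, CAPS d = 0.55).* With PCL d = 0.40, noncentrality is 0.40 × √30 = 2.191 and power for the pair is 55% to 59%. With PCL d = 0.70, noncentrality is 3.834 and power for the pair is 84% to 85%.

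**4. Check by simulation.** With 40,000 simulated trials of 60 per arm analysed by t-tests, at ρ = 0.5, 0.7 and 0.9, the two-sided either-win error was 8.9%, 8.2% and 7.1%, and both-win power was 75.7%, 77.8% and 80.8%.

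**The case against.** The best defence is that the sample size section names a single outcome at a single time, and that N, alpha and power all follow from it. If CAPS alone decides, nothing is inflated and nothing is lost. This shows what the trial was sized for, but it does not settle the rule: the same section goes on to analyse PCL under the primary-outcome heading, and Sections 2.0 and 5.0 name it as primary.

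A second defence is that the hypothesis joins the measures with *and*, which suits a both-must-win rule better than an either-win rule. That is a fair reading, but no passage states it and no power is shown for the pair.

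Three points about size stand:

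- The hypothesis is directional, so the relevant either-win error is 3.5% to 4.5% against 2.5%; the two-sided 7.0% to 9.1% includes false results favouring the control. If the correlation is indeed strong, the upper ends of these ranges are less likely.
- A power shortfall under a both-must-win rule is not established. It depends on PCL's effect and on the gain from baseline adjustment; at r = 0.5 the pair has 89% to 91%, above the stated 85%.
- The bias contrast is one of degree. A blinded rater limits rater bias, but the CAPS answers still come from unblinded participants.

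None of these supplies the missing rule.

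**Conclusion.** The concern holds, with high confidence. The sections conflict on whether there is one primary outcome or two, and no rule links the two 4-month tests to the primary hypothesis. The sample size arithmetic itself is sound. The stated 5% error and 85% power are assured together, on the plan's own assumptions, only if CAPS alone decides. The inflation in the either-win case and the lower power in the both-win case are alternatives that cannot apply together, and their sizes rest on correlations and a PCL effect that the documents do not give. This should be fixed before outcome data are seen, but it does not undermine the design.

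**What to change.** Before outcome data are seen, reconcile Sections 2.0, 5.0 and 8.0 as follows.

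- State that CAPS total at 4 months is the single primary endpoint, tested at two-sided 0.05.
- Test PCL at 4 months at two-sided 0.05 only if CAPS is significant. This fixed sequence holds the error across the pair at 5%.
- Label the 8-week and 7-month contrasts, which the plan already describes as early and sustained response, as secondary, and say whether they join the false discovery rate family.

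This follows the choice the sponsor made when sizing the trial. It costs a few sentences and no participants: N = 232 and the stated alpha and power for CAPS are unchanged. The price is that a win on PCL alone could not be called a primary success.

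A stated both-must-win rule would also remove the ambiguity and keep PCL as co-primary. The sponsor would then have to show power for the pair, with explicit assumptions for the PCL effect and the correlation.
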